10. DATA COLLECTION AND OUTCOME MEASURES

All measurements and sample collection will be conducted by trained, certified staff. Any measure-specific devices, instruments, and equipment will be calibrated and standardized. All lab measures will be analyzed in the same labs, and all patient-reported outcomes will be captured by standardized forms. Eligibility, baseline, and follow-up data will be collected by phone, over the web, and at in-person visits. To the extent possible, questionnaire data will be collected through website (for the coach-directed arm) or telephone, rather than on-site. Inperson data collection visits will be conducted mainly at ProHealth, with satellite sites at SKCCC and Johns Hopkins Bayview if needed. Below are the primary and secondary measures that will take place at specific contact points across all arms.

Data Collection Schedule

Table 3: Data Collection Schedule, All Participants

	Prescreen	Screening	Randomization	3 months	6 months	12 months
Data collection						
Eligibility/Interest	X	X				
Informed consent	X	X				
Weight		X		X	X	X
Height		X				
Blood pressure		X	X	X	X	X
IGF-1/IGFBP-III		X	X	X [§]	X [§]	X [§]
Metabolic Panel labs		X		X	X	X

CBC		X				X
HbA1c [§]			X		X	X
CRP. IL-6, IL-8			X		X	X
Stored specimens [†]			X		X	X
Stool Sample			X		X	X
Randomization			X			
Questionnaires						
Demographics		X				
Diet/physical activity		X		X	X	X
Eurol-Qol		X		X	X	X
Medical history		X				
Medications		X	X	X	X	X
Interim events			X	X	X	X

§ Processed as a batch from frozen specimens. † Stored.

Primary Outcome Measure

Insulin-like Growth Factor I (IGF-1): At each in-person visit, participants will be asked to have fasted for at least 9 hours. Phlebotomy, processing, and storage will be done by trained staff members and according to a standardized protocol. Frozen samples will be transported to the University of Maryland School of Medicine Pathology Laboratory where assays for IGF-1 will be conducted using the IMMULITE 2000 Assays.

Insulin-like Growth Factor Binding Protein III (IGFBP-III): At each in-person visit, participants will be asked to have fasted for at least 9 hours. Phlebotomy, processing, and storage will be done by trained staff members and according to a standardized protocol. Frozen samples will be transported to the University of Maryland School of Medicine Pathology Laboratory where assays for IGFBP-III will be conducted using immunoassays

Secondary Outcome Measures

Height: This is a onetime measure during the first in-person visit. Participants will stand straight without shoes, and a standard calibrated wall mounted stadiometer will be used. Precision of height is up to 0.1 of a centimeter.

Weight: At each in-person visit, staff blinded to randomized assignments will measure weight while the participant is shoeless and in light clothing. A calibrated, standardized electronic weight-measuring scale will be used. Measurements are in pounds and later converted to kg for analysis. Weight will be measured twice; if the difference between the two measures is more than 0.1 kg, then another measure will be taken.

Body Mass Index: BMI will be calculated as (weight in kg/height² in meters)

Other Outcome Measures

Lipids: Total cholesterol, triglycerides, and HDL will be measured from overnight fasting plasma. LDL will be calculated by the Friedewald equation.

Glucose and Insulin: Fasting glucose and insulin will be measured after overnight fasting from plasma.

HbA1c: HbA1c measures will be measured from whole blood.

Demographics and Medical History: A self-reported assessment of basic patient characteristics will be collected which will include age, gender, race/ethnicity tobacco use, , health insurance status, , income, employment, education level, post-menopausal status and current health status and co-morbid conditions (e.g., diabetes and hypertension). Additional details on solid tumor malignancy will also be obtained, including organ of origin, date of diagnosis, stage of disease at diagnosis, treatments received, and date of completion of treatment(s).

Diet and Physical Activity: Diet will be assessed with standardized questionnaires. Physical activity will be assessed by both a standardized questionnaire and an accelerometer.

- Fruit & Vegetable Screener is a brief self-report measure of daily fruit and vegetable intake, portion size, frequency and type.
- Block Fat Screener is a brief self-report assessment of percent energy intake from fat; this measure comes from the National Cancer Institute's Risk Factor Monitoring and Methods staff.
- Physical Activity will be measured using the Godin Physical Activity Measure. It will be used to estimate levels of moderate and vigorous physical activity from the previous week.
- 87,88.87 91,92

Quality of Life: The EuroQol measure is drawn from the EQ-5D measure and has 6 questions. The EQ-5D descriptive system consists of five dimensions: 1) mobility; 2) selfcare; 3) usual activities; 4) pain/discomfort; 5) anxiety/depression.

Current Medications: Current medication use will be assessed by self-report of medication names, dosages, routes of intake and frequency.

Serious Adverse Events will be measured using the Serious Adverse Event Form (SAEForm). This form measures the event, characteristics, onset, and severity.

IL-6, IL-8 , both will be measured using commercial sandwich-based enzyme linked immunosorbent assays (ELISAs).

hs-CRP will be analyzed by quantitative immunoturbidimetry.

Stored Specimens

Serum and plasma samples of all our participants will be stored at -80°C for future investigation of other studies. In addition, fecal samples will be collected at baseline visit, and 6th month. Samples will be transported on dry ice to N2 Vapor Freezers or Mechanical Ultra Low Freezers (-80°C) in the Tissue Bank of the Hopkins Conte Digestive Diseases Basic and Translational Research Core Center for long-term storage and analysis at a later time.

Future measures: the following are future measures that are not supported by this trial:

- leptin, adiponectin, VEGF, HGF, and EGF; SLC22A1, SLC22A2, and SLC47A1 gene variants; and 16S bacterial whole genome sequencing of gut microbiome.

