All potential participants will demonstrate the ability to send and receive emails, ability to complete online forms, and sufficient phone minutes for coaching calls during this visit.

Screening Visit 2

Participants, who remain eligible after the screening visit 1, will be asked to attend the second screening visit after at least 9 hours of fasting. The following activities and measurements will take place:

- Orient the participant about each intervention arm, expectations and related details. -
Weight
- Blood pressure
- Fasting labs
- HbA1c
- Current medication
- Questionnaires (See Table 3)

Randomization Visit

During this visit, study staff will reconfirm the eligibility. Weight and blood pressure will be measured. Each participant will be re-oriented to each intervention arm. Each participant will be randomized and assigned to one of the three interventions arm: self-directed weight loss, coach-directed behavioral weight loss or metformin.

Follow-Up Visits

There are three types of follow-up based on the contact mode: in-person, telephone and website.

In-person follow-up visits will take place at ProHealth at 3-month, 6-month, and 12-month intervals. Participants will be asked to attend those visits after having fasted for at least 9 hours. The following will take place during these visits:

- Weight
- Blood pressure
- Fasting labs and HbA1c
- Patient reported outcomes (EuroQol;)
- Current medication

- Fat screener, fruit screener, physical activities, general symptoms form
- Pill counts for adherence, challenges and enabling factors for adherence
- Any adverse events
- Any other issues raised by the participant that can be addressed within the scope of the study

Additional telephone contacts, for the metformin arm, will take place at the following times after baseline visit: every 2 weeks for the first month and otherwise as needed throughout the intervention period. During these calls, the study staff will ask about adherence and side effects using a standardized study questionnaire.

Throughout the study, email and web contacts will take place to remind participants in the coach-directed behavioral weight loss arm to enter their self-monitoring data, and to followup on adherence and check for adverse events. In-person visits will take place on the 3rd, 6th and the twelfth month for the same reasons.

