14. DATA AND SAFETY MONITORING

14.1 Data Management System

All information will be collected through the study website or using case-report forms. All studyrelated data will be reviewed for accuracy by the Project Manager or Database Manager. A periodic review will be done by the data analysis team.

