17.2 General Statistical Approach

The primary endpoint of this trial is the 6-month change in level of IGF-1 and IGF1 to IGFBP-III ratio among the Coach-Directed Behavioral Weight Loss arm versus self-direct arm (B vs. A), and metformin arm compared to self-direct arm (C vs. A). Intervention effects will be analyzed using intent-to-treat. Each active intervention arm will be compared with the control arm using

likelihood based mixed effects linear regression models utilizing data from all 3 time points, i.e. baseline, 6, and 12 months, simultaneously, as following.

The primary analysis model: The mean model for the mixed effects regression will be structured to include 2 binary intervention arm indicators (for Group B and C), 3 binary followup time indicators (for 3-, 6- and 12-month follow-up), and the cross-product interaction terms between the group and time indicators (6 interaction terms), and the covariance model will employ a 4x4 unstructured covariance matrix to allow different outcome variances and account for the intra-individual outcome correlations over time. Race and baseline BMI levels, the variables used for stratifying the randomization, will be included in the mean model. Other variables found not to be balanced between the trial arms will also be included as necessary. Outcomes may be transformed as needed to satisfy the distributional assumptions for the likelihood approach.

The primary testing contrasts of this trial will be the 2 aforementioned pairwise comparisons at 6 months, which will be evaluated through the regression coefficients of the Group B by 6month interaction term (B vs. A), and Group C by 6-month interaction term (C vs. A), respectively. The secondary testing contrasts include B vs. C of change in outcomes at 6month, and the 3 pairwise group comparisons of outcome changes at 12 months, which will be evaluated using the same model through the corresponding group by time interaction terms.

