For outcomes such as IGF-1, IGF-1:IGFBP3 ratio, weight, BMI, and measures assessed through the metabolic panel labs, where data will be available at 3-month, these information will be utilized through the primary model to enhance model estimation, especially in the event of missing data encountered at 6- and/or 12-month, events though the effect size of the intervention at 3-month is not part of the primary or secondary goals. For outcomes such as EQ-5D, questionnaire outcomes on dietary intake and physical activity, HbA1c, IL-6, IL-8, and CRP, where data will not be available at the 3-month visit, the analysis models will not include any independent variables terms related to that visit.

We will also conduct subgroup analyses to explore for potential differential intervention effects across these pre-specified subgroups. Statistical significance of these subgroup analyses will be evaluated though incorporating appropriate subgroup by intervention by visit interaction terms. To explore the association of physical activity levels with the outcomes of IGF-1 or the IGF-1: IGFBP-3 ratio, time dependent physical activity measures will be further included to augment the primary analysis model to explore for the degree of attenuation of intervention effect by physical activities. Similar analyses could be done for body weight and BMI.

We will also explore for possible treatment effect modification by baseline BMI level to better understand the potential heterogeneity of treatment effects to inform future trials and studies. This will be carried out by including the 3-way interaction terms (Group indicator by Time indicator by BMI) in the primary analysis model. We will also estimate total intervention costs for future trials in a large population.

Missing and incomplete data

Prevention is far superior to a statistical cure, and every effort will be made to collect outcome data on all randomized participants. For example, we will collect outcomes on individuals who have stopped participating in the trial intervention. Due to the high longitudinal correlation, missed “interior” visits won’t decrease information very much for a linear trend. However, they are needed to assess departures from a linear trend.

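### Section 10's preferred questionnaire mode depends on arm, Section 9 lists the same questionnaires at in-person visits, and no rule makes the mode common to all three arms

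*Combined protocol and SAP*

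**What the plan says.** Section 10 opens with general rules for data collection. Patient-reported outcomes are to be captured on standardized forms, and follow-up data may come by phone, web or in-person visit. It then states a preference: "To the extent possible, questionnaire data will be collected through website (for the coach-directed arm) or telephone, rather than on-site". The coach-directed arm is the only arm named.

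Section 9 (Follow-Up Visits) begins "There are three types of follow-up based on the contact mode: in-person, telephone and website". Its list of what happens at the in-person visits at 3, 6 and 12 months includes "Patient reported outcomes (EuroQol" and "Fat screener, fruit screener, physical activities, general symptoms form". Neither item is limited to an arm. Table 3, whose title covers all participants, schedules the diet/physical activity and EuroQol questionnaires and has no column for mode.

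Aim 5 names EuroQol, dietary intake and physical activity as outcomes at 6 and 12 months. Section 17.2 reads intervention effects from the "cross-product interaction terms between the group and time indicators".

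**The concern.** Section 10 steers questionnaires away from the clinic and names a web route for one arm. Section 9 places the same instruments at the clinic visit. Neither section says which governs, and none requires the mode to be the same across arms or to be recorded.

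People can answer the same question differently on a web form, to an interviewer by telephone, or at a clinic. If the mode mix differs by arm after randomization, part of an arm difference in a self-reported outcome may come from the mode. The outcomes concerned are EuroQol, diet and questionnaire physical activity. The comparisons concerned are coach-directed versus self-directed (B vs A) and coach-directed versus metformin (B vs C).

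**Working it through.** The plan gives no figure to reproduce. The check compares the texts and then follows a mode effect through the model.

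1. **Preferred mode.** Section 10: website, named for arm B, or telephone, in preference to on-site. This is qualified as applying where possible.
2. **Listed setting.** Section 9: the same instruments at the in-person visit. The list names no arm. It also contains pill counts, which concern only metformin, so it is a generic list. The title of Table 3 supports reading it as covering all arms.
3. **Common rule.** Sections 9, 10, 11, 14.1 and 17.2 contain none. The standardization in Section 10 applies to the form, not to how it is administered.
4. **Baseline.** Section 7 places randomization after all screening and baseline data collection, and Table 3 puts diet/physical activity and EuroQol at screening. Baseline mode therefore cannot depend on the assigned arm.
5. **Follow-up.** Take on-site as the reference. Let mW and mT be the average shifts in a score due to web and telephone, assumed additive and equal in all arms. Let pW and pT be the shares of questionnaires collected by each mode in an arm at a given follow-up. The baseline mode term is the same in expectation in every arm and cancels. The mode part of the B vs A difference in change is then

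   mW × (pW in B − pW in A) + mT × (pT in B − pT in A).

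   - Section 9 followed in every arm: all shares are 0, so the mode part is 0.
   - Same mode mix in both arms: 0.
   - Modes equivalent (mW = mT = 0): 0.
   - Section 10 followed, with a fraction f of arm B on the web, the rest of B by telephone, and all of A by telephone: mW × f + mT × (1 − f) − mT = f × (mW − mT).

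   B vs C has the same form with C in place of A. For C vs A, Section 10 writes in no difference: with no web use in either arm, the term is mT × (pT in C − pT in A), which is 0 unless the telephone shares happen to differ.
6. **Model.** The expression in step 5 falls in the group-by-time coefficients. Race and baseline BMI, the planned covariates, do not remove it.

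The documents give no value for mW, mT or any share, so no numerical size follows.

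The 6- and 12-month scope comes from Aim 5. Section 17.2 describes EQ-5D and the diet and activity questionnaires as outcomes "where data will not be available at the 3-month visit", while Table 3 and Section 9 schedule them then. That is a separate discrepancy, and this point does not depend on it.

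**The case against.** The best defence is that Section 10 states only a preference and that Section 9 allows flexible data collection. A preference set against a visit list is an ambiguity. A reader might infer a flat contradiction; the qualified wording does not support that. The flexibility clause does not settle the matter, however: its examples concern splitting or bundling visits, not choosing a mode by arm.

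The restriction to arm B also has a plausible reason. The study website is the intervention platform of that arm (Section 8.2), so Section 10 may only be saying who has access. That explains the wording but leaves its effect on mode in place.

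Several stronger readings are tempting and are not supported:

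- **Section 14.1 as a third, conflicting default.** "All information will be collected through the study website or using case-report forms" describes data capture. It is compatible with web entry for one arm and paper forms for telephone or on-site answers.
- **Bias in the symptoms form.** Table 3 has no row for that form, so no baseline is documented, and Section 17.2 does not name it among the modelled questionnaires.
- **A built-in mode difference for metformin.** The extra calls in Section 9 are scheduled in the first month and then as needed, and "During these calls, the study staff will ask about adherence and side effects using a standardized study questionnaire". Nothing makes them the route for EuroQol, diet or activity at 6 or 12 months.
- **Unmasking of follow-up staff.** An arm-specific route could reveal the arm, but the documents do not describe the workflow.
- **A material bias.** Any figure in SD or standard-error units would rest on invented mode effects, web shares and correlations.

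Finally, participants know their arm. A common mode would remove only the mode part of any reporting difference. That limits the gain but does not justify adding a mode difference.

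**Conclusion.** The concern holds as a minor point. The stated preference can itself produce a mode difference between arms after randomization, so this is more than missing detail. Where it is followed, any mode effect enters B vs A and B vs C for EuroQol, diet and questionnaire physical activity at 6 and 12 months.

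The size is unknown and may be zero. The documents do not say whether on-site forms are self-completed, or how often the preference would be followed given that all arms attend the visits. The conclusion rests on two conditions: Section 10 is followed to different degrees or by different routes across arms, and mode affects the answers.

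IGF-1, the IGF-1:IGFBP-3 ratio, weight, BMI and accelerometer data are not collected by questionnaire and are not affected.

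**What to change.** Reconcile Sections 9 and 10. Suggested text for Section 10:

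> At each follow-up at which they are collected, outcome questionnaires use the same primary mode in all three arms. The same back-up mode applies under the same rule in every arm. The mode of each assessment is recorded and reported by arm.

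Name the primary mode: either on-site at the visit already required, or one online form open to every arm and kept separate from the coach-directed intervention site. The Section 9 visit list should refer to this rule.

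Any mode-adjusted analysis should be labelled exploratory. Mode is determined after randomization and partly by the participant, so adjusting for it can itself introduce bias. If mode coincides with arm, the two effects cannot be separated at all.

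The cost is low: wording in two sections and one mode field on the form. On-site collection makes visits slightly longer. Online collection needs a small amount of set-up, and is feasible because Section 5.1 requires every participant to be able to complete online forms. Either choice gives up some of the flexibility in Section 9, and the common back-up rule limits that loss.

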11. MASKING OF DATA COLLECTION

Upon confirmation of eligibility and baseline data collection, 120 participants will be randomized in a 1:1:1 ratio to one of the three intervention arms. Randomization will be stratified by race and baseline BMI. Password-protected randomization software will ensure authorized access to the group assignment, which is restricted to designated study personnel only during the execution of the trial. The randomization scheme will be generated by the biostatistician. Intervention assignment is not blinded to the trial participants, nor the intervention staff. However, study staff involved in follow-up data collection will be masked to the randomization assignments. Moreover, the primary outcomes will be measured by labs; and staff in the lab will be blinded to the randomization assignment.

12. DISCONTINUATION OF SUBJECTS

Reasons for discontinuation and withdrawal will be documented in participant's medical record. All study interventions expected to last for 12 months, unless the participant fulfills one or more of the following conditions:

- Diagnosis of new or recurrent illness that may require the participant to stop the intervention, based on the judgment of the principal investigator.
- Diagnoses of recurrent cancer that may require a change in therapy plan, which may prevent the participant from continuing the study's specific intervention.
- Pregnancy
- Patient request to discontinue due to inability to take or tolerate metformin

Reimbursement

Participants enrolled and randomized in the intervention study arms will receive \$50-150 compensation in check for every follow-up visit for a possible total of \$300. Participants who need transportation, cost may be compensated.

13. ADVERSE EVENT

13.1 General

National Cancer Institute/Common Terminology Criteria for Adverse Events (CTCAE) v4.0 will be the guideline for this study in describing, grading, and reporting of adverse events. Adverse events believed to be related to weight loss or metformin will be reported. Adverse event information will be collected during each in-person visit from screening phase onward. Only adverse events possibly, probably or definitely related to study interventions will be tabulated and reported according to NIH guideline (insert reference). All serious adverse events, regardless of relation to study interventions must be reported to the principle investigator. All adverse and serious adverse events will be reported to the local institutional review board. Any modification to consent and/or study protocol, resulting from an adverse event, will be provided to IRB with the report of the adverse event.

Definitions

- Adverse event (AE): Any undesirable sign, symptom, or medical condition occurring after starting therapy, even if the event is not considered to be related to the study. An undesirable medical condition can be symptoms (e.g., nausea, chest pain), signs (e.g., tachycardia), or abnormal results of a procedure (e.g., laboratory findings, biopsies).

Medical conditions/diseases present before starting study treatment are only considered adverse events if they worsen after starting study treatment and are believed to be related to the weight loss or metformin intervention.

- Serious adverse event or reaction: Any untoward medical occurrence secondary to therapy that: results in death, is immediately life-threatening, requires inpatient hospitalization or prolongation of existing hospitalization, results in persistent or significant disability, or is an important medical event that may jeopardize the subject or may require medical intervention to prevent one of the outcomes listed above.

The definition of a serious adverse event (experience) also includes an *important medical event*. Medical and scientific judgment should be exercised in deciding whether expedited reporting is appropriate in other situations, such as important medical events that may not be immediately life-threatening or result in death or hospitalization but may jeopardize the patient or may require intervention to prevent one of the other outcomes listed in the definition above. These should also usually be considered serious.

A hospitalization planned before the start of the study agent(s) and/or for a preexisting condition that has not worsened does not constitute a serious adverse event (e.g., elective hospitalization for breast reconstruction). A hospitalization for a social reason in the absence of an adverse event also does not meet the criteria for a serious adverse event.

- Unexpected adverse event: An adverse event, which varies in nature, intensity or frequency from information on the investigational intervention provided in the Investigator's

Brochure, package insert, or safety reports. Any adverse event that is not included in the informed consent is considered “unexpected”.

- Expected (known) adverse event: An adverse event, which has been reported in the Investigator’s Brochure. An adverse event is considered “expected”, only if it is included in the informed consent document as a risk.

Relationship

An investigator will assess the relationship between adverse events to study intervention as follows:

- Definitely: An adverse event, which has a timely relationship to the administration of the investigational drug/agent, follows a known pattern of response, for which no alternative cause is present.
- Probably: An adverse event, which has a timely relationship to the administration of the investigational drug/agent, follows a known pattern of response, but for which a potential alternative cause may be present.
- Possibly: An adverse event, which has a timely relationship to the administration of the investigational drug/agent, follows no known pattern of response, but a potential alternative cause does not exist.
- Unlikely: An adverse event which does not have a timely relationship to the administration of the investigational drug/agent, follows no known pattern of response, does not reappear or worsen after re-administration of the investigational drug/agent (if applicable), and for which there is evidence that it is related to a cause other than the investigational drug/agent.
- Unrelated: An adverse event, for which there is evidence that it is definitely related to a cause other than the investigational drug/agent. In general, there is no timely relationship to the administration of the investigational drug/agent, or if there is a timely relationship, the event does not follow a known pattern of response, and there is an alternative cause.

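### Only adverse events judged related are to be tabulated, and no all-cause adverse event summary by randomized arm is stated

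*Combined protocol and SAP*

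**What the plan says.** Section 13.1 sets the tabulation rule: "Only adverse events possibly, probably or definitely related to study interventions will be tabulated and reported according to NIH guideline". It also says, more briefly: "Adverse events believed to be related to weight loss or metformin will be reported".

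What is collected is wider. The definition of an adverse event covers any undesirable sign, symptom or condition after the start of therapy, "even if the event is not considered to be related to the study". Collection is not limited to one arm: "Adverse event information will be collected during each in-person visit from screening phase onward". Section 9 lists adverse events among the items for the 3-, 6- and 12-month visits, and Table 3, which covers all participants, has a row for interim events. One exception narrows the definition: worsening of a pre-existing condition counts only if it is thought to be related to the weight loss or metformin intervention.

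Case reporting is also wider than the table. Section 13.1 sends all adverse and serious adverse events to the IRB, and all serious events to the principal investigator whatever their cause.

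On attribution, section 13.1 says: "An investigator will assess the relationship between adverse events to study intervention as follows". Five categories follow. On masking, section 11 says: "Intervention assignment is not blinded to the trial participants, nor the intervention staff". It masks the staff who collect follow-up data, and the laboratory staff.

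Section 17 names no adverse event analysis. The only descriptive summary by arm that it specifies is of baseline characteristics.

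**The concern.** In a randomized trial, event rates can be compared between arms without anyone deciding what caused each event. The self-directed arm supplies the background rate. A table limited to events judged related gives up that advantage, because the background rate is passed through a judgement that may be made differently in each arm.

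Two features of this trial make that likely to matter. Treatment is open to participants and intervention staff. And the relatedness scale is written for a drug, although two of the three arms receive none. Nausea on metformin matches a side effect listed in section 13.2. The same nausea in the self-directed arm cannot, on a literal reading, have a timely relationship to a drug that was not given.

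The primary IGF-1 analysis is untouched. At stake is whether the trial's safety table supports a fair comparison between arms.

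**Working it through.** The plan gives no figure to reproduce here. The check is of the text, followed by an illustration.

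**1. Collection, reporting and tabulation side by side**

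| Step | Scope | Where |
|---|---|---|
| Definition | Regardless of cause, except pre-existing conditions | 13.1 |
| Collection | In-person visits, every arm | 9, 13.1, Table 3 |
| Case reports to the IRB | All adverse and serious adverse events | 13.1 |
| Case reports to the principal investigator | All serious events | 13.1 |
| Tabulation | Possibly, probably or definitely related only | 13.1 |
| Statistical analysis | None stated for adverse events | 17 |

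The restriction enters at tabulation and is not lifted in the analysis section.

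**2. The relatedness scale**

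All five definitions (*Definitely*, *Probably*, *Possibly*, *Unlikely*, *Unrelated*) name the investigational drug or agent. Participants not assigned it: 40 + 40 = 80 of 120, or 67%. This describes the wording and is not a measure of bias.

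Take a timely event with no known response pattern and a potential alternative cause:

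- *Definitely* and *Probably* require a known pattern, so they do not fit.
- *Possibly* requires that the event "follows no known pattern of response, but a potential alternative cause does not exist", so it does not fit.
- *Unlikely* requires an event that "does not have a timely relationship to the administration of the investigational drug/agent", so it does not fit.
- *Unrelated* opens by asking for evidence of a definite other cause. Its second sentence then admits a timely event without a known pattern if an alternative cause is present.

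The event lands at or near *Unrelated*. Either way it is left out of the table.

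**3. What a related-only table can do (illustration)**

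Let pC and pA be the all-cause event rates in the metformin and self-directed arms, and qC and qA the shares judged related.

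- True difference = pC − pA
- Tabulated difference = pC·qC − pA·qA
- Distortion = pA(1 − qA) − pC(1 − qC)

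The distortion is zero only if the same fraction of participants leaves the table in each arm.

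From the documents: 40 per arm (section 17.1), and 28% of people on metformin reporting gastrointestinal side effects (section 13.2). Assumed: that 28% is the all-cause rate, and every value of pA, qC and qA. With qC = 100%:

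| pA | True difference | Tabulated, qA = 0 | qA = 50% | qA = 100% |
|---|---|---|---|---|
| 5% | 23 points | 28 | 25.5 | 23 |
| 10% | 18 points | 28 | 23 | 18 |
| 20% | 8 points | 28 | 18 | 8 |

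The error can also run the other way:

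- pA = 5%, qC = 80%, qA = 50%: 22.4 − 2.5 = 19.9 points tabulated, against 23 true.
- pA = 20%, qC = qA = 50%: 14 − 10 = 4 points tabulated, against 8 true.

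With no true difference (20% in each arm, 8 against 8 of 40):

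- qC = 50%, qA = 25%: 4 against 2 tabulated, a false difference of 5 points.
- qC = 50%, qA = 0: 4 against 0, a false difference of 10 points.
- qC = qA = 50%: 4 against 4, no false difference.

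**The case against.** **The rule may not define the safety analysis.** The sentence sets a reporting rule under an NIH guideline whose reference is an unfilled placeholder. It does not say that the table is by arm. Section 14.3 provides for annual review by a safety monitoring committee, and section 15 mentions reports to a DSMB and clinician review of adverse events, without giving their content. This stands as a limit: one can say that no all-cause summary by arm is stated, not that none will ever be made. But the related-only rule is the only tabulation rule given.

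**A between-arm symptom comparison is planned.** Aim 5 lists a side effects questionnaire as an outcome at 6 and 12 months, and section 9 adds a general symptoms form at follow-up visits. This stands in part. The questionnaire may give an attribution-free comparison, perhaps including gastrointestinal symptoms, though its items are not shown. It does not cover adverse or serious adverse events as such, and section 17 gives it no method.

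**Differential attribution is not shown.** Follow-up data collectors are masked, and the documents do not say whether the investigator who judges relatedness is. This stands: the bias is plausible, not demonstrated. The scale is nonetheless hard to apply without knowing who received the drug.

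**The coach-directed arm is covered.** The reporting sentence names weight loss, and the lead-in to the scale refers to the study intervention. This also stands. The mismatch is between that lead-in and the five definitions under it.

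**Conclusion.** The concern holds in a limited form. Followed as written, the plan yields a table filtered by attribution and states no all-cause adverse event or serious adverse event summary by arm, although most of the data for one are collected. Such a table can overstate or understate differences between arms. How far depends on background rates and attribution rates that the documents do not give, so the figures above show direction and possibility only.

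Four stronger readings are tempting, and the documents do not support them:

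- That unrelated events go unrecorded or unreported. They are collected, and all go to the IRB.
- That the metformin excess would be inflated by a particular factor. Any such factor comes from the assumed attribution rates, and the error can be zero or reversed.
- That some events fit no relatedness category. The second sentence of *Unrelated* nearly covers the case in question; what remains is an ambiguity between a potential and an actual alternative cause.
- That the trial has no attribution-free safety comparison at all. The Aim 5 questionnaire may provide a partial one.

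A separate inconsistency in section 13.1 also needs attention. The serious-event definition requires the event to result from therapy, while the reporting rule for serious events disregards relation. Read strictly, the definition removes the unrelated events that the rule is meant to capture.

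**What to change.** - In sections 13.1 and 17, state that all adverse events and all serious adverse events will be tabulated by randomized arm regardless of attribution, with relatedness as a secondary column.
- Base the comparison between arms on events collected at the common 3-, 6- and 12-month visits. Section 9 adds telephone calls in the metformin arm and email and web contacts in the coach-directed arm that also ask about side effects or adverse events, and it describes no equivalent for the self-directed arm. List events found only through those contacts separately.
- Word all five relatedness definitions around the study intervention, and make clear where a timely event with a potential alternative cause belongs.
- Reconcile the serious-event definition with the rule that serious events are reported whatever their cause.
- Preferably, record worsening of pre-existing conditions regardless of believed cause.

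The cost is protocol and SAP wording and a longer table with more unrelated events in it. No extra visits are needed. Recording worsening of pre-existing conditions regardless of cause, and flagging how an event was detected, may need a small change to the case-report form, because the documents do not show that either is captured now.
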